#### 5. Outcomes.

The primary outcome is documented receipt of high-quality care at the time of the appointment or within 30 days of the appointment (see Table 1). The items below will be added together to form a score and the number of items completed out of the total will be the primary outcome measure compared across groups. We will measure these data for all patients with SLE, osteoarthritis, and inflammatory arthritis including RA seen by the provider during the 6-month study period as well as do a separate subgroup analysis focused on the patients who had their appointments audiorecorded. We will use electronic medical record data obtained from chart review, from RPDR and from the Enterprise Data Warehouse (EDW) to obtain these metrics.

Table 1. Quality metrics for diseases of interest		
Systemic lupus erythematosus (SLE)	Rheumatoid Arthritis (RA)	Osteoarthritis
Hydroxychloroquine (HCQ) initiation If lupus nephritis, immunosuppressive initiation, ACE-I or ARB, glucocorticoids Glucocorticoid prophylaxis (e.g. PPI, calcium/vitamin D, PJP if high dose) Contraception if on teratogenic medication Vaccinations Baseline HCQ eye exam and monitoring labs	DMARD initiation, or bDMARD initiation Folic acid if receiving methotrexate Glucocorticoid prophylaxis Contraception if on teratogenic medication Baseline X-rays, TB and hepatitis screening Labs within 1 month of methotrexate initiation Documentation of disease activity measure Vaccinations	Annual functional status assessment Baseline exams Annual pain assessment Recommendation for assistive devices

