## 2. Patients

Patients who consent to participate will be asked to have one clinical encounter with their provider recorded (preferably the next appointment) and then to complete a set of baseline surveys following that encounter including demographics, social determinants of health, everyday discrimination experiences, satisfaction with care, patient trust in the medical profession, patient perception of care centeredness and medication adherence. Surveys can be completed either via REDCaps via a link sent securely to the patient, or on paper forms (and then will be entered into REDCap by our study team). We will also assess medication adherence again 3 months after the encounter using a survey or a brief phone call, and over the 6-month period using the proportion of days covered data now available in the EMR. Patients will receive a \$30 gift card or e-check once the surveys are completed. We will also collect data from the patients' charts. These data include: demographics, social determinants of health, comorbidities/diagnoses, quality metrics related to their rheumatic disease, lab results, preventive care use (including immunizations), healthcare utilization (including ED visits, hospitalizations, outpatient visits and appointment no shows), medication use (including use of contraception as a quality metric), and medication refill data (proportion of days covered, available in the EMR) over the 6 months following the date of the recorded encounter. We will review the note from the date of the encounter and determine whether the individuation statement was documented in the intervention group.

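### The primary score closes 30 days after the visit, but the methotrexate lab item runs one month from drug start, so labs that meet the metric can lose credit

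*Combined protocol and SAP*

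**What the plan says.** Section 6.5 (Outcomes) defines the primary outcome as documented receipt of high-quality care "at the time of the appointment or within 30 days of the appointment". It adds the Table 1 items into a score, so that "the number of items completed out of the total will be the primary outcome measure compared across groups". It does not say whether the total is every listed line or only the lines that apply to the patient.

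Table 1 rewards drug initiation: "Hydroxychloroquine (HCQ) initiation" for lupus and "DMARD initiation, or bDMARD initiation" for rheumatoid arthritis. It also lists items that apply only once a drug is in use. One of these has its own clock, "Labs within 1 month of methotrexate initiation". Others have none, for example "Folic acid if receiving methotrexate" and "Baseline HCQ eye exam and monitoring labs".

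Two other places matter. Section 3 allows prior records to be reviewed for one-time or infrequent screens. Section 6.2 (Patients) collects chart data "over the 6 months following the date of the recorded encounter", and section 6.3 (Chart reviews) uses the same period. No section says how an item still open at day 30 is scored.

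**The concern.** The score's window is anchored to the appointment, and the methotrexate lab item is anchored to the start of the drug. Initiation earns credit on any day from 0 to 30, so the two clocks agree only for a start on the visit day. For every later start the score closes before the item's own period has ended. The look-back in section 3 does not help, because these labs fall due after the visit.

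Two things are at stake. Patients whose care equally meets the metric can be scored differently only because of the day the drug was started, and two abstractors could score the same chart differently. Also, initiation is behaviour that the score rewards and that the intervention may increase. If it does, more intervention patients will carry a truncated item, and the observed arm difference will shrink. The trial enrols patients seen at most twice in the past year, including those referred on high suspicion of disease (section 4, 2B), so new starts are plausible.

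**Working it through.** **Step 1. The plan's own figure.** Inputs from section 9: 10 providers per arm, difference 0.5 SD, two-sided alpha 0.05. Effective n per arm = 10m / [1 + (m − 1) × ICC]. Power = Φ(0.5 / √(2/n) − 1.96).

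- ICC 0.02, m = 8: 80 / 1.14 = 70.2, power 84.2%.
- ICC 0.05, m = 10: 100 / 1.45 = 69.0, power 83.6%.

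The stated 84% reproduces in both cases with the normal approximation. It does not depend on the scoring window and is not challenged here.

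**Step 2. The two clocks.** Day 0 is the appointment, and 1 month is taken as 30 days. For a start on day d the item's deadline is d + 30, and the score sees 30 − d days of that period.

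| Start day | Item deadline | Days of the lab period inside the score window |
|---|---|---|
| 0 | 30 | 30 |
| 7 | 37 | 23 |
| 14 | 44 | 16 |
| 21 | 51 | 9 |
| 30 | 60 | 0 |

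A start on day 14 with labs on day 40 meets the item as worded (26 days after start) but lies 10 days outside the score window.

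**Step 3. Loss of credit for one such patient**, if day 30 is applied literally:

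- All eight rheumatoid arthritis lines as denominator: 1/8 = 12.5 percentage points.
- Six applicable lines (DMARD, folic acid, baseline X-ray/TB/hepatitis, labs, disease activity, vaccinations), all done: 5/6 = 83.3% instead of 100%, a loss of 16.7 points.

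The loss occurs under either denominator.

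**Step 4. Does starting the drug lower the score?** Use applicable items, and let the patient who is not started score a/b, with initiation counted in b and missed. Starting, with k triggered items unmet, gives (a + 1)/(b + k). This is below a/b only if a/b > 1/k.

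- k = 1: never lower. Examples are 1/2 to 2/3, 3/4 to 4/5 and 4/5 to 5/6.
- k = 2: lower only from above 50%, for example 3/4 to 4/6 (75% to 67%).

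Only the methotrexate lab item has a clock running from drug start, so k = 1 is the case that the documents support. In the six-line example, not starting gives 3/4 = 75%; starting with folic acid done and labs lost gives 5/6 = 83%. With a fixed denominator, starting adds no item at all.

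**Step 5. Effect on the comparison.** The documents give no initiation rates, start-day distribution or item completion rates. As an assumption only, shrinking the 0.5 SD effect by 10%, 20% or 30% (to 0.45, 0.40 or 0.35 SD) would lower power to 76.0%, 65.9% or 54.5% at ICC 0.02 and m = 8.

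**The case against.** The strongest reply is that the specific wording governs the general. The lab item states its own period, so an abstractor reading Table 1 as written would credit day-40 labs after a day-14 start. That reading is reasonable, but the plan does not adopt it. The 30-day limit is stated for the outcome as a whole, with no exception for this item. At the least, a primary-outcome rule is left to the abstractor.

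A second reply is that a 30-day window applied equally to both arms is a legitimate prespecified outcome. This stands for the other items. It does not reconcile an item whose definition runs past that window.

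A third is that the 6-month period in sections 6.2 and 6.3 starts from the recorded encounter, which most chart-review patients do not have. The wording is loose, but the healthcare utilization outcome in section 6.5 includes those patients and counts 6 months from the encounter of interest. Follow-up to day 60 is therefore within the planned collection.

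A reader might infer more than the documents support:

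- **That starting a rewarded drug is penalised.** Step 4 shows that it is not with one open item.
- **That follow-through items in general cannot be finished in time.** Folic acid, contraception and glucocorticoid prophylaxis can be documented at the visit, and labs after a day-0 start fit the window.
- **That the hydroxychloroquine eye exam fails in the same way.** The documents give no time to examination, and the section 3 look-back may credit an earlier exam.
- **That the bias has a known size.** Assume 20 percentage points more starts, a 16.7-point loss in 25% to 100% of the extra starters, and an SD of 20 points. The arm difference then shrinks by 0.20 × 0.25 × 16.7 = 0.8 to 0.20 × 16.7 = 3.3 points, or 0.04 to 0.17 SD. None of these inputs is in the documents. The osteoarthritis column has no drug-start item, which would dilute the effect further.

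**Conclusion.** The two clocks conflict for one item of the primary score. For any methotrexate start after the visit day, the score closes before the item's own deadline, by up to 30 days. Applied literally, the window denies 12.5 or 16.7 points to a patient whose labs meet the metric after day 30, depending on the denominator.

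Across the trial, this under-credits some new starters. If initiation rates and start days are similar in both arms, the main result is noise and inconsistent scoring. If the intervention raises initiation, the arm difference is attenuated. Its size cannot be derived from the documents. The conclusion rests on reading the 30-day limit as covering every item and on taking 1 month as 30 days. It does not rest on the eye exam, and it leaves the 84% power figure intact. The point merits correction before analysis because it concerns a stated rule for the primary outcome.

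**What to change.** - Keep the 30-day window for initiation and the other items. For any methotrexate start inside that window, score the lab item within 1 month of the recorded start date, using the 6-month chart data. The latest deadline is about day 60.
- State whether the denominator is all listed items or applicable items only.
- For the hydroxychloroquine eye exam, keep the primary rule and report completion by 6 months as a sensitivity analysis. Do not credit an order or referral in the primary score, because that would replace receipt of care with ordering.
- State that follow-up for patients in the chart review only is counted from the index appointment.
- Apply the rules identically in both arms and fix them before arm-level data are seen.

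This changes scoring only, not care. It needs a few sentences in section 6.5 and no new data source. The downside is that scoring of some new starters finishes up to about 30 days later.

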#### Secondary outcomes:

- 1) Change in provider IAT scores pre and post intervention. [name] at VCU will participate in this. She will submit to VCU for IRB approval for participation using completely deidentified data. A Data Use Agreement is in process between the two institutions.
- 2) Differences in perception of patient centeredness, patient satisfaction, patient trust in the medical profession, experiences of discrimination and adherence (at time of visit and at 3 months) comparing the intervention to non-intervention group. This secondary outcome is only for that patients enrolled in the study (not the chart review-only non-interaction group). We will additionally measure adherence for a full 6 month period using the proportion of days covered measure now available through the EMR both for participants in the survey component and for the chart review patients.
- 3) Healthcare utilization – we will compare ED visits, hospitalizations, outpatient visits completed and outpatient visit no shows between the two arms in the 6 months following the encounter of interest. We will include chart review patients (non-interaction) as well as patients who consented and had audiorecorded encounters in this part.
- 4) Provider communication (measured only for patients enrolled in the study who had their appointment audiorecorded). Provider communication will be measured using the recorded transcripts and compared between arms: a) physician-to-patient talk time ratio, b) physician word use (number of first person pronouns, and number of positive and negative emotion-related words, divided by all words in the interaction) and c) total length of interaction. This part of the study will be led by [name] (VCU). [name] will have a Data Use Agreement to receive de-identified transcripts for this analysis and separate IRB approval through her institution to work with these deidentified qualitative data.

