### **3. General Description of Study Design**

We will conduct a cluster-randomized controlled trial. The clusters are 20 rheumatologists at multisite BWH and MGH-affiliated clinics. Rheumatologists will be stratified by hospital and by gender and randomly assigned. Ten rheumatologists will be assigned to the intervention arm and ten to the control. Assessments will be conducted for 8-10 patients per rheumatologist (max 100 patients total in each arm, 200 total). Randomization will be stratified by BWH and MGH Rheumatology main campus hospitals (MGH or BWH/ Faulkner (FH)) and their rheumatology satellite clinic sites, and by provider gender (male or female). Study schema is included as an attachment.

In addition to the 200 SLE, osteoarthritis, and inflammatory arthritis patients including RA who will be studied directly, we also will examine the medical records of patients with inflammatory arthritis, osteoarthritis, or SLE in the practices of the enrolled providers seen during the same study period. In addition to the chart review of patients who meet the inclusion criteria of less than 2 visits in the past year, we will perform a secondary analysis of all patients who may have been seen greater than 2 times in the past year as we anticipate a spillover effect from the intervention and would like to study

this. Patients who were approached to participate in the audiorecorded component of the trial and declined will not be included in this medical record review. We will have no direct interaction with these patients. Most medical records we will review will be for patients of enrolled providers who we had no direct interaction with. The goal of this chart review component is to more broadly examine the impact of the intervention on the quality measures described in Table 1 below, beyond those individuals who will have their encounters audiorecorded. In addition to allowing for a larger sample size for analysis, it also will allow for analyses that may not be influenced by the act of recording an encounter (e.g., possibly, due to the recording, care may be somewhat different from other patients in each providers' practice and this will allow us to capture both). For quality metrics that would only be a onetime screen or once every few years, we will review prior records to see if they were eligible for those outcomes (such as receipt of vaccinations).

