## 6. STUDY PROCEDURES

### 1. Providers

Providers will be recruited and those who consent will be stratified by gender and site and randomized to the intervention or control arm. All providers in both arms will be asked to complete demographic surveys (either paper or on REDCap (with link sent using "Send Secure with the text "Please follow the below link to respond to the survey questions. Thank you for your participation.") and four Implicit Association Tests (IATs). Two of the tests assess biases related to race and two parallel tests assess biases related to socioeconomic status. As this is an interactive tool, we have instead attached the exact terms and instructions that will be used as an attachment. For each of the IATs, providers will be presented with a screen that has either the "cooperative" or "not cooperative" or "good" or "bad" linked with either "Black" or "White" for the race IATs and linked with "rich" or "poor" for the SES IATs. Providers will be prompted to, for example, click left for a bad term or photograph of Black individual, and right for a good term or photograph of a White individual, and then this will be reversed. The same will occur for the SES terms. IATs are standardized, well-accepted tools for measuring implicit bias (<https://implicit.harvard.edu/implicit/takeatest.html>). Millisecond

software/Inquisit web will be used to administer the tests because it allows for assessment of reaction time for correct classification, which is essential to IATs. Random IDs will be created using RedCAP or Qualtrics that are different from the participant IDs and will be stored on Millisecond/Inquist without any identifiable information. All identifiable information will be stored within the MGB Firewall on RedCap. After providers take the IATs and complete the baseline demographics form (under attachments), both arms will be given the link to freely available brief unconscious bias training module

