≥1 month after providers take the IATs, we will begin the process of recording 8-10 provider-patient interactions within each providers’ practice. This will occur at BWH or MGH Rheumatology main campus and satellite clinic sites. Providers will also be immediately informed before a patient encounter that will be recorded and will have the opportunity to decline. We anticipate encounters to last between 20-40 minutes. The vast majority of rheumatology outpatient encounters include only the provider and patient but if any other person is in the room (e.g., an observing medical resident), they will be asked for their permission as well. To record, a digital voice recorder (this one, or an equivalent from the MGB approved Staples vendor: [https://www.staples.com/Gpx-Pr047b-Digital-Voice-Recorder/product\\_2699228](https://www.staples.com/Gpx-Pr047b-Digital-Voice-Recorder/product_2699228)) or an MGB-encrypted iPad will be used (placed in the room by a research team member with both patient and provider aware, and collected immediately following the encounter), and all data will be transferred to the project-specific MGB secure drive at the end of each day and then

deleted from the device. For the iPad, the recording will be saved directly onto MGB Dropbox (and the MGB Dropbox app will also be used for the recording). These files will be transcribed verbatim using an MGB-approved vendor and all identifiable information will be removed. After 6 months, which is our estimate for recruitment time, providers will be asked to repeat the IATs. After completion of the study, providers will receive a one-time \$50 gift card or e-check.

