## 9. Statistical Analysis

Power calculations are based on Aim 1's primary outcome (quality metric score). We account for an intracluster correlation coefficient (ICC) of 0.02 among patients of the same provider and assume a two-sided alpha level of 0.05. With 10 providers in each arm (N=20) and 8 patients per provider (N=160), we would have 84% power to detect a mean difference between arms of 0.5SD. If the ICC is 0.05, we would have 84% power to detect the same mean difference if 10 patients per provider were included.

All analyses will follow intention-to-treat (ITT) principles. All analyses will follow intention-to-treat (ITT) principles. For Aim 1, unadjusted and adjusted linear generalized estimating equation (GEE) models that account for patient clustering by providers will be used, with the quality metric score as the primary dependent variable, intervention arm as the primary predictor variable and covariates including hospital, and other factors that are either strongly correlated with the dependent variable (e.g. rheumatic disease) or imbalanced between the arms. We will use Millisecond software to program the IATs and calculate D scores that reflect response times and compare these findings across the two groups. For Aim 2, unadjusted and adjusted linear GEE models will be constructed with a) communication metrics and b) models for each survey score as the dependent variables, intervention arm as the primary predictor variable, and covariates as above. We will also analyze the transcripts qualitatively using Dedoose software and use the constant comparison method to evaluate and refine our themes and our codes.

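### The IAT comparison in about 20 providers has no stated model; adjusting for the baseline D score and the randomisation strata would be a low-cost gain in precision over raw change

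*Combined protocol and SAP*

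**What the plan says.** - **Outcome.** Section 6.5, under secondary outcomes, lists first "Change in provider IAT scores pre and post intervention".
- **Analysis.** Section 9 says the software will be used to "calculate D scores that reflect response times and compare these findings across the two groups". The GEE models and the covariate rule in that section are written for the quality score, the communication metrics and the survey scores. Nothing says how the baseline IAT score, hospital or gender enters the IAT comparison.
- **Sample.** Section 3: "The clusters are 20 rheumatologists at multisite BWH and MGH-affiliated clinics", and "Ten rheumatologists will be assigned to the intervention arm and ten to the control".
- **Data collected.** Section 6.1 has both arms take four IATs at baseline, two on race and two on socioeconomic status, before the bias module and the individuation meeting. Later it says: "After 6 months, which is our estimate for recruitment time, providers will be asked to repeat the IATs".
- **Randomisation.** Sections 5 and 6.1 stratify by site and gender, not by IAT score. They describe randomisation before the baseline IATs.

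**The concern.** With 10 providers per arm, the chance difference in mean baseline score between arms has a standard error of 0.45 SD. Under equal SDs, a raw change score subtracts the whole of that difference, whereas only a fraction r of it is expected to persist to 6 months. The remaining (1 − r) goes into the effect estimate through regression to the mean. Baseline adjustment estimates the slope instead of fixing it at 1.

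What is at stake is the width of the confidence interval for each of the four IAT effects, and the freedom to choose between post score, raw change and adjusted change after the data are seen. The primary outcome is not affected.

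**Working it through.** **The plan's own figure.** Section 9 gives power only for the quality score: 84% for 0.5 SD. It reproduces. With 8 patients per provider and ICC 0.02, the design effect is 1 + 7 × 0.02 = 1.14, effective n per arm is 80/1.14 = 70.2, and the normal approximation gives 84.2%. With 10 patients and ICC 0.05, the design effect is 1.45, effective n is 100/1.45 = 69.0, and power is 83.6%. For the IAT outcome there is no power, SD, effect size or pre-post correlation to reproduce.

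**Inputs.** n = 10 per arm and N = 20 (Section 3). Two-sided alpha of 0.05 is borrowed from the primary power statement in Section 9. Assumed here: the same SD at both times, a common linear slope, complete data, and r between 0.3 and 0.9.

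**Formulas** (variance of the arm difference, in SD² units):
- Raw change: 2(1 − r) × 2/n, with 18 df.
- Adjusted for baseline: (1 − r²) × 2/n × (1 + 1/(N − 4)), with 17 df. The last factor, 17/16, is the cost of chance baseline imbalance and an estimated slope.
- Adjusted for baseline, hospital and gender, with strata balanced and unrelated to the score: the factor becomes 1 + 1/14 = 15/14, with 15 df.
- Effect detectable with 80% power (noncentral t): 2.963, 2.973 and 2.998 times the standard error at 18, 17 and 15 df.

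**Example, r = 0.5.** Raw change: 2 × 0.5 × 0.2 = 0.200, SE 0.447, detectable 2.963 × 0.447 = 1.32 SD. Baseline-adjusted: 0.75 × 0.2 × 17/16 = 0.159, SE 0.399, detectable 2.973 × 0.399 = 1.19 SD. Variance ratio: 0.159/0.200 = 0.80.

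| r (assumed) | Variance, change | Variance, baseline-adjusted | Reduction | Detectable, change | Detectable, baseline-adjusted | Detectable, with hospital and gender too |
|---|---|---|---|---|---|---|
| 0.3 | 0.280 | 0.193 | 31% | 1.57 | 1.31 | 1.32 |
| 0.5 | 0.200 | 0.159 | 20% | 1.32 | 1.19 | 1.20 |
| 0.7 | 0.120 | 0.108 | 10% | 1.03 | 0.98 | 0.99 |
| 0.8 | 0.080 | 0.077 | 4% | 0.84 | 0.82 | 0.83 |
| 0.9 | 0.040 | 0.040 | −1% | 0.59 | 0.60 | 0.60 |

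**Break-even.** The variance ratio is (1 + r)/2 × 17/16. It equals 1 at r = 32/17 − 1 = 0.88.

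**Simulation check** (20,000 trials per r, true effect 1 SD). Power for raw change against baseline adjustment was 43% and 58% at r = 0.3, 57% and 66% at r = 0.5, 77% and 82% at r = 0.7, and 99.7% and 99.6% at r = 0.9. The simulated variance ratios were 0.69, 0.80, 0.89 and 1.01.

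**Chance imbalance.** The SE of the baseline difference is √(2/10) = 0.447 SD. A one-SE imbalance shifts the raw-change estimate by (1 − r) × 0.447, which is 0.31, 0.22 or 0.13 SD at r = 0.3, 0.5 or 0.7.

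**The case against.** **No model is named.** A reader might infer that the plan commits to analysing raw change. The documents do not say that. Section 6.5 gives an outcome label and Section 9 leaves the model open. Change regressed on arm and baseline gives the same arm estimate and standard error as the 6-month score regressed on arm and baseline, so the label does not rule out the better analysis. This stands. The point is therefore that the text invites an unadjusted comparison and specifies nothing better.

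**The gain could be overstated.** The large-sample variance ratio, (1 + r)/2, would suggest reductions of 35%, 25% and 15% at r = 0.3, 0.5 and 0.7, and that adjustment never loses. With 20 providers neither is right: the reductions are 31%, 20% and 10%, and at high r the lost degrees of freedom outweigh the saving. This stands too, and the table uses the small-sample figures. The loss at r = 0.9 is trivial, so it is not a reason to leave baseline out.

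**Completeness.** A reader might assume two scores for every provider. Section 6.1 says only that providers will be asked to repeat the tests, so 20 is an upper limit.

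**Importance.** The outcome is secondary, and Section 1 says that reducing provider bias is not the primary aim. At r = 0.3 to 0.7, only effects of about 1 SD or more are detectable under either analysis. This limits the priority but does not remove the gain.

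**Conclusion.** The concern holds as a low-priority improvement. The IAT analysis is unspecified, and its natural reading is an unadjusted comparison of change in 20 providers. Adjusting for a baseline score that is already planned would cut the variance of the arm effect by about 31% at r = 0.3, falling to 4% at r = 0.8, with nothing gained above about 0.88. These figures rest on an assumed r, equal SDs and complete data, none of which the documents settle.

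The documents do not support saying that the plan has chosen a wrong model, or that adjustment would make this comparison well powered. Nor does any trial conclusion depend on it. The benefit is a narrower interval at most plausible correlations and a choice fixed in advance, which is useful in a pilot meant to inform a larger study.

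**What to change.** In Section 9, state that for each of the four IATs the 6-month D score will be analysed by linear regression on arm, the same test's baseline D score, hospital and gender, with the arm effect reported with its 95% confidence interval. The outcome can keep its name as change, because regressing change on the same terms gives the same arm estimate. State how many providers contribute both scores.

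Section 6.1 should also confirm that providers take the baseline IATs before learning their arm. Randomisation is described first, and a baseline score affected by knowledge of allocation would compromise the change score and the adjusted analysis alike.

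The cost is a sentence or two in Section 9 and a clarification in Section 6.1. No new data are needed. The model uses 3 more degrees of freedom than an unadjusted comparison (15 instead of 18).
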